7.1 Risks and Benefits

Human participants' involvement and characteristics. COVID-infected adults 18 years of age and older who are enrolled in the prospective COVID-19 Host Immune Response Pathogenesis (CHIRP) cohort for Aims 1 & 2, and acute COVID-positive individuals 18 years of age and older who completed a Phase 2a trial of disulfiram (IND 151837, NCT04485130) from the UCSF CHIRP cohort.

Sources of materials. Research materials include questionnaire and biospecimen data (serum, plasma, PBMCs, nasopharyngeal swabs, saliva) stored in the UCSF Core Immunology Lab and UCSF AIDS Specimen Bank CHIRP repository will be used to perform new assays as part of the experiments described in this proposal. Data will be identified by participants pre-existing de-identified study number.

All laboratory specimens, evaluation forms, reports, and other records that leave the site will be identified by coded number so that participant confidentiality can be maintained. All records will be kept locked. All computer entry and networking programs will be performed with coded numbers only.

There are no direct benefits to the study participants. However, there are some potential secondary benefits. However, the results from this study may eventually benefit other SARS-CoV-2-infected individuals in the future. This study may provide data to help identify novel therapeutic strategies for treating COVID-19. Participants will be reimbursed to cover costs related to the study (travel, loss of time). The knowledge gained from the proposed study has the potential to impact clinical care and research efforts with regard to individuals infected with SARS-CoV-2.

7.1.1 Potential risks

Confidentiality: Participation in research may involve loss of privacy. Participant's records will be handled as confidentially as possible. All research records will be coded with a four-digit study ID code. Only the study investigators and their staff will have access to study records and test results. Study charts will be kept in a locked file cabinet in a locked office. Electronic data will be protected with a password and kept on a secure network on the UCSF Fresno Network server.. All collaborators will receive specimens only identified by the four-digit study ID. No individual identities will be used in any reports or publications resulting from this study.

Disulfiram: Disulfiram is an irreversible inhibitor of sulfhydryl-containing enzymes resulting in inhibition of ALDH and in the accumulation of acetaldehyde after ingestion of ethanol. It is FDA-approved as a pharmacotherapy for alcoholism. Side effects reported with disulfiram include drowsiness, peripheral neuropathy, hepatotoxicity, seizures, optic neuritis, hypertension, and metallic or garlic-like taste in the mouth. Adverse events associated with disulfiram administration are relatively infrequent occurrences with the proposed FDA approved doses, but we will mitigate against such events by thorough medical history-taking and examination as well as close clinical monitoring during the testing and by the brief duration of administration (up to 5 days total). We will repeat liver function tests at the conclusion of the

studies. Disulfiram produces an aversive reaction to ethanol due to the rapid accumulation of acetaldehyde in the blood. This reaction is characterized by flushing, diaphoresis, palpitations, nausea, vomiting, and sometimes, hypotension. This may last for up to 5 hours and in some cases the reaction has been complicated by myocardial infarct, heart failure, and death. Such reactions will be minimized through education and close clinical monitoring of participants. Participants will also be instructed to abstain from alcohol during disulfiram administration and for two weeks after finishing these studies. They will also be instructed to avoid inadvertent alcohol exposure through various alcohol containing products. Participants are given an Emergency Card that lists disulfiram as a current medication and provides contact information for study investigators. Participants have access to study investigators 24 h/d, 7 d/week for any medical issues or questions that may arise.

Risk of Pregnancy for Women of Childbearing Potential: Women of childbearing potential are not excluded from these studies. They must have a plan for avoiding pregnancy while on study protocol and this is discussed with each woman during the assessment process. We also test women for pregnancy in the medical workup for study entry. A woman would be discharged from the study if the test were to be positive and referred to standard prenatal care. The effects of disulfiram on an unborn baby are unknown. All participants will be counseled to use two forms of birth control during the study. Females of childbearing potential must have a negative pregnancy test at screening and agree to use a double-barrier method of contraception throughout the study period.

Safety measures

Recruitment and informed consent: Informed consent for phlebotomy will be obtained as part of the consent for enrollment into the disulfiram trial. This study has been reviewed by Community Medical Centers Institutional Review Board. All participants will be informed of the discomforts, risks, and benefits of blood sampling

Monitoring: Participants will be monitored carefully throughout the study. At each visit, participants will be assessed for any new symptoms and vital signs will be obtained by a study coordinator.

Protection against risks: Research records will be confidential to the extent permitted by law. Participants will be identified by a code, and personal information from study records will not be released without the participant's permission. Study participants will not be identified in any publication about this study.

7.2 Definitions

Adverse Event (AE): Any untoward medical occurrence in a clinical investigation participant who has received a study intervention and that does not necessarily have to have a causal relationship with the study product. An AE can, therefore, be any unfavorable and unintended sign (including an abnormal laboratory finding, for example), symptom, or disease temporally associated with the use of the study product, whether or not considered related to the study product.

Serious Adverse Event (SAE): Any adverse event that results in any of the following outcomes:

- Death
- Life-threatening (immediate risk of death)
- Prolongation of existing hospitalization

- Persistent or significant disability or incapacity
- Important medical events that may not result in death, be life threatening, or require intervention or escalation of care may be considered a serious adverse event when, based upon appropriate medical judgment, they may jeopardize the participant and may require medical or surgical intervention to prevent one of the outcomes listed in this definition. Examples of such medical events include allergic bronchospasm requiring intensive treatment in an emergency room or at home, blood dyscrasias or convulsions that do not result in inpatient hospitalization.

Unexpected Adverse Event (UAE): An adverse reaction, the nature or severity of which is not consistent with the investigator's brochure.

Serious and Unexpected Suspected Adverse Reaction (SUSAR): An adverse reaction, the nature of which is not consistent with the investigator's brochure with severity as defined by SAE above.

Unanticipated Problem (UP): Unanticipated Problem that is not an Adverse Event (e.g. breaches of confidentiality, accidental destruction of study records, or unaccounted-for study drug).

Protocol Deviation: Deviation from the IRB-approved study procedures. Designated serious and non-serious

Serious Protocol Deviation: Protocol deviation that is also an SAE and/or compromises the safety, welfare or rights of participants or others

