5.3 Study Population

5.3.1 Inclusion Criteria

1. Willing and able to provide written informed consent, and
2. Age \geq 18 years, and
3. Recent symptomatic COVID-19 disease (<14 days from symptom onset)

4. Recent SARS-CoV-2 positive test by molecular diagnostic assay within the preceding 7 days, and
5. Not currently hospitalized, and
6. Willing to abstain from any alcohol during the two-week period in which disulfiram will be administered and during the two-week period immediately after disulfiram administration.
7. Both male and female participants are eligible. Females of childbearing potential must have a negative pregnancy test at screening and agree to use a double-barrier method of contraception throughout the study period.

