5.3.8 Prohibited medications

For study days 1-31, use of medications that are considered standard-of-care at the study site (including antiviral medications available under Emergency Use Authorization) is permitted. Use of other medications with potential anti-SARS-CoV-2 activity, including off-label, expanded access, or investigational agents, should be discussed with the team.

Note: Participants who are hospitalized during the study are eligible to receive COVID-19 treatment per local standard of care, including remdesivir, immunomodulatory agents and/or convalescent sera/plasma and will not be excluded from the study if receiving this standard of care. Azithromycin administered for treatment of presumed or confirmed infection will be permitted.

After study day 31, use of anti-COVID-19 treatments as salvage therapy for those with persistent severe COVID-19 are permitted but should be recorded.

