7.3.3 Assessment of Seriousness

Event seriousness will be determined according to the protocol definition of an SAE.

Event severity will be graded using the DAIDS toxicity table
<https://rsc.niaid.nih.gov/sites/default/files/daidsgradingcorrectedv21.pdf>

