7.3.4 Assessment of Association

The association assessment categories that will be used for this study are:

- **Associated** – The event is temporally related to the administration of the study product and no other etiology explains the event.
- **Not Associated** – The event is temporally independent of the study product and/or the event appears to be explained by another etiology.

The investigator must provide an assessment of association or relationship of AEs to the study product based on:

- Temporal relationship of the event to the administration of study product
- Whether an alternative etiology has been identified
- Biological plausibility
- Existing therapy and/or concomitant medications.

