8.1 Criteria for Discontinuation of the Study

Two cohorts of participants (N=30 each) will be sequentially enrolled and receive disulfiram daily for five days at doses of 1000mg or 2000mg. The independent Safety Monitoring Committee will review the safety and tolerability data after the first cohort has completed dosing and determine whether it is safe to proceed with enrolling the final cohort using the below criteria.

In addition, the study enrollment and dosing will be stopped and an ad hoc review by the SMC will be performed if any of the specific following events occur or, if in the judgment of the study physician, participant safety is at risk of being compromised:

- a. Death within one hour of drug administration
- b. Occurrence of a life-threatening allergic/hypersensitivity reaction (anaphylaxis), manifested by bronchospasm with or without urticaria or angioedema requiring hemodynamic support with pressor medications or mechanical ventilation, TRALI, TACO.
- c. One participant with an SAE associated with study product.
- d. Two participants with a Grade 3 or higher lab toxicity for the same parameter associated with study product. (Grading will be assessed using DAIDS Toxicity Table <https://rsc.niaid.nih.gov/sites/default/files/daidsgradingcorrectedv21.pdf>)
- e. An overall pattern of symptomatic, clinical, or laboratory events that the SMC considers associated with study product and that may appear minor in terms of individual events but that collectively may represent a serious potential concern for safety.
- f. Any other event(s) which is considered to be a serious adverse event in the good clinical judgment of the responsible physician. This will be appropriately documented.

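### The SAE list in Section 7.2 covers a prolonged hospital stay but not a new admission, in a trial that enrols only non-hospitalized patients

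*Combined protocol and SAP*

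**What the plan says.** All references are to the combined protocol and SAP.

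- **Population.** Section 5.3.1 requires entrants to be "Not currently hospitalized, and" (the list of criteria continues). Section 5.3.8 looks ahead to admissions: "Participants who are hospitalized during the study are eligible to receive COVID-19 treatment per local standard of care". Section 5.1.2 makes the proportion hospitalized a secondary objective.
- **SAE list.** Section 7.2 gives five outcomes: death, a life-threatening event, "Prolongation of existing hospitalization", lasting disability or incapacity, and important medical events as judged by the investigator.
- **Use of the list.** Section 7.3.3 states: "Event seriousness will be determined according to the protocol definition of an SAE". The SUSAR definition in 7.2 borrows the same list, "with severity as defined by SAE above". Trigger 8.1(c) is "One participant with an SAE associated with study product".
- **Association.** Section 7.3.4 has two categories. An event is Associated when "The event is temporally related to the administration of the study product and no other etiology explains the event". It is Not Associated when it is temporally independent of the product and/or "the event appears to be explained by another etiology". The adverse event log (5.7, Table 4) has five levels of relatedness, from definitely related to not related. Section 6.1 counts events at the top three of those levels.

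**The concern.** No participant has a hospital stay to prolong on entry, so the one hospitalization criterion cannot capture the event that matters most in this setting: an outpatient who has to be admitted after dosing. If that event is not an SAE by definition, three things that depend on the SAE label become unreliable: the SAE count, SUSAR classification, and the trigger that stops enrollment and dosing on a single associated SAE. The SMC uses the Section 8.1 criteria to decide whether to open the 2000 mg cohort, so the definition bears on dose escalation as well as on reporting.

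The association rule raises a related but smaller issue. Triggers 8.1(c) and (d) turn on whether an event is associated. The site records relatedness on a five-level form, and the protocol never says which of those levels amount to associated.

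**Working it through.** The plan states no figure on this point, so the check is a reading of the sections against one another, with counts.

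**1. Does any criterion name a new admission?** Of the five criteria in 7.2, one mentions hospitalization as an outcome and none names a first admission.

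**2. Trace a hypothetical case.** Suppose a participant at home on day 3 of dosing becomes confused, is admitted for two nights, is never in danger of death and recovers fully.

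| 7.2 criterion | Met? |
|---|---|
| Death | No |
| Life-threatening | No |
| Prolonged existing stay | No, there was no stay to prolong |
| Disability or incapacity | No |
| Important medical event | Only if judged so; the wording is permissive |

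The SAE label rests entirely on the last row. The examples in that row are events that did not lead to admission, which presupposes that events leading to admission are caught elsewhere in the list. They are not. This looks like an omission rather than a choice.

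**3. What does the label control?**

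| Use | Section |
|---|---|
| Number of SAEs, a safety endpoint | 6.1 |
| SUSAR definition | 7.2 |
| Stop and ad hoc SMC review on one associated SAE | 8.1(c) |
| Ongoing SMC monitoring; other adverse events wait for scheduled meetings | Synopsis, Planned Interim Analyses |

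**4. What remains without the label?** Trigger 8.1(f) covers any other event that the responsible physician considers serious. The 8.1 lead-in stops the study if the study physician judges safety at risk. Neither needs the 7.2 list or an Associated rating, and both lead to the same stop and ad hoc review as 8.1(c). The protocol team reviews all events weekly (7.4.1), the SMC reviews cohort 1 safety data before escalation (8.1), and admissions are recorded as a secondary outcome. All of these would let someone see the admission. None makes it an SAE by rule.

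**5. Compare the relatedness scales.**

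| AE log level (5.7) | Counted as related in 6.1 | Place in 7.3.4 |
|---|---|---|
| Definitely | Yes | Associated, by natural reading |
| Probably | Yes | Not stated |
| Possibly | Yes | Not stated |
| Unlikely | No | Not stated |
| Not related | No | Not Associated, by natural reading |

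Three of the five log levels have no stated place in the rule that drives 8.1(c) and (d).

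**6. Does the cut-off matter?** This step is illustration only, because the documents give neither input. Let *p* be the assumed rate of SAEs at least possibly related to drug, *s* the assumed share of them ruled Associated, and take the 20 participants on disulfiram in one cohort. The chance that 8.1(c) fires is 1 − (1 − *ps*)^20.

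| *p* | *s* = 1 | *s* = 0.5 |
|---|---|---|
| 2% | 1 − 0.98^20 = 33% | 1 − 0.99^20 = 18% |
| 5% | 1 − 0.95^20 = 64% | 1 − 0.975^20 = 40% |
| 10% | 1 − 0.90^20 = 88% | 1 − 0.95^20 = 64% |

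The cut-off can change how often the trigger fires. The table does not say which cut-off is right, because some of the extra stops would be for events caused by COVID-19.

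**The case against.** The strongest reply is that 8.1(f) and the study-physician clause already give the same stop and the same ad hoc review, and that 8.1(c) is not free of judgment either, since 7.3.2 leaves seriousness and causality to the site investigator. To slip through, an admission thought to be drug-related would also have to be judged not serious under 8.1(f). This stands, and it makes the consequence smaller. It does not restore the SAE count or the SUSAR definition, and it replaces a rule with discretion.

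A second reply is that the list breaks across a page just after the quoted item, so a line may have been lost when the text was extracted. The item itself is intact and nothing shows a missing line, but the original page should be checked first.

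On association, 7.3.4 asks whether another cause explains, or appears to explain, the event, not whether one could. Having COVID-19 does not by itself explain a given event, and the investigator must also weigh timing, biological plausibility and other medication. A stricter threshold for stopping than for tabulation is not in itself an error. That also stands: the defect is the missing link between the scales.

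A reader might infer more than the documents support:

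- *That drug-related admissions would go unseen, or could not stop the trial.* The backstops in step 4 of the working rule that out.
- *That possibly related events are barred from 8.1(c) and (d).* The text leaves their status open.
- *That the earlier 2000 mg disulfiram and vorinostat trial (4.1.8), halted after events rated possibly and probably related, shows this rule would have failed.* Those participants also took vorinostat, the planned course was 28 days rather than 5, and the seriousness of the events is not stated. Section 4.1.8 also reports no Grade 2–4 events among 30 participants on disulfiram alone at up to 2000 mg.

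**Conclusion.** The point holds for the SAE definition. Read literally, Section 7.2 leaves a new admission outside the SAE list in a trial where admission is provided for and nobody enters as an inpatient. The loss is confined to the SAE label, with the count and the SUSAR definition that depend on it, and to the rule-based trigger 8.1(c). The size of the effect cannot be estimated: the documents give no admission rate and no basis for saying how many cases the discretionary routes would catch. The conclusion assumes that the extracted list is complete.

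The mismatch in relatedness scales is real but secondary. It calls for a stated link between the scales. Whether *possibly related* should be enough to stop dosing in a blinded COVID-19 trial is a matter of judgment, and the documents do not settle it.

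This should be fixed because the correction is short and concerns safety, not because there is evidence that harm would be missed.

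**What to change.** **Primary.** Check the original page of 7.2 for a lost line. If there is none, put *inpatient hospitalization or* in front of the existing prolongation item. No other section needs rewording, since 6.1, the SUSAR definition, 7.3.3 and 8.1(c) all follow from the list. The cost is SAE paperwork for admissions due to COVID-19. Such an admission would not fire 8.1(c) unless it were also rated associated. It would help to add a sentence saying that 8.1(f) remains a matter of clinical judgment, so that an admission plainly due to COVID-19 is reported as an SAE without automatically pausing the trial.

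**Secondary.** Use the five-level scale of the adverse event log throughout and state which levels count as associated for 8.1(c) and (d). Agree the cut-off, for example *possibly* or *probably*, with the SMC before dosing starts. The lower cut-off matches 6.1 and misses fewer signals, but a single ambiguous admission could then halt enrollment and dosing, and under blinding that includes admissions on placebo. The higher cut-off does the reverse. Either is workable once written down; the cost is protocol wording and case report form guidance.

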7.3 Safety Reporting Requirements

7.3.1 Reporting Interval

All AEs and SAEs will be documented from the first administration of study product. All AEs and SAEs will be followed until resolution even if AEs extend beyond the study-reporting period. Resolution of an adverse event is defined as the return to pre-treatment status or stabilization of the condition with the expectation that it will remain chronic. At any time after completion of the study, if the investigator becomes aware of a SAE that is suspected to be related to study product.

7.3.2 Investigator's Assessment of Adverse Events

The determination of seriousness, severity, and causality will be made by an on-site investigator who is qualified (licensed) to diagnose adverse event information, provide a medical evaluation of adverse events, and classify adverse events based upon medical judgment. This includes but is not limited to physicians, physician assistants, and nurse practitioners.

Laboratory abnormalities will be reported as AEs if there is a 2 standard deviation increase above baseline.

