The total volume collected during the study is 406 mL and does not exceed the Red Cross limit of 500 mL. Safety labs collected during these visits will be monitored, and volume will be decreased at the discretion of the PI if needed. The blood volumes in this study were carefully calculated to stay within Red Cross Guidelines. This is the approach that is taken in HIV interventional trials, and indeed, the PK sampling days can be tricky. Even for observational (non-interventional trials), there are large volume protocols with separate Informed Consent, for example, the HIV SCOPE cohort that allows a much larger blood draw in a single day for the type of research assays being performed for DISCO. Indeed, most of the whole blood is processed and cryopreserved for several years to be applied towards future assays that have yet to be discovered at this time. In a recent project, 202 HIV+ samples were pulled, that were collected in the 1990s from the SCOPE cohort to be applied to advanced host whole genome sequencing assays that we now have available today.

This trial is not only looking at clinical outcomes. The mechanism by which disulfiram acts is not well understood but based on [name] recent data in Nature Immunology- this drug may have important implications not just for SARS-CoV-2, but other infectious pathogens that trigger an aberrant inflammatory response. If we are going to ask these study participants to take a study drug, we would like to understand HOW it is working, which may point to upstream novel drug targets that may be even more effective down the line in treating COVID-19. Each research assay requires approximately 10 cc of whole blood (Ficolled into PBMCs, peripheral blood mononuclear cells). Some assays require 2 aliquots.

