6 STATISTICAL PLAN

6.1 Sample Size and Power Considerations

Based on a design with 20 patients per disulfiram treatment group within each dosing cohort (1000 mg, 2000 mg) and a null hypothesis that there will be a differential change in plasma inflammatory cytokine levels (e.g., IL-6) in both groups (disulfiram treatment and placebo compared to baseline), we use reported ranges of plasma IL-6 levels in COVID-19 disease¹¹⁹ to estimate sample size and power. Based on a mean plasma IL-6 level of 36.7 pg/mL (95% CI 21.6-62.3 pg/mL), we estimate that the study will have approximately 80% power to detect a 35% difference in plasma IL-6 levels between the disulfiram versus placebo groups. These measurements will be assessed at day 5, 15 and 31 at the 0.05 significance level using a log-likelihood ratio test and non-linear mixed effect regression modeling. This estimate is based on the assumptions that plasma IL-6 levels are log normally distributed and that the standard deviation of the pre- and post-dose levels is 12 ng/mL (derived from ref: DE Leisman et al. Cytokine elevation in severe and critical COVID-19: a rapid systematic review, meta-analysis, and comparison with other inflammatory syndromes). The adjustments will be made for pre-treatment plasma inflammatory cytokine (e.g., IL-6) levels. Safety endpoints will include the total number of Grade 2 or higher events; the number of Grade 2 or higher events possibly, probably or definitely related to study drug; the number of serious adverse events; and the number and cause for treatment or study discontinuation.

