6.2.1 Primary endpoint

- Changes in plasma inflammatory biomarker levels² (e.g., IL-6, IL-1 β) at days 5, 15, and 31.

6.2.2 Secondary endpoint(s):

- Safety and tolerability (frequency of Grade 2 or higher adverse events) at days 2, 3, 4, 5, 7, 9, 11, 15, and 31.
- Change in SARS-CoV-2 PCR quantitative viral load⁴ at days 5, 15, and 31.
- Change in COVID-19 clinical stage (five-point symptom severity scale³) at days 5, 15, and 31.
- The proportion of detectable versus not detectable levels of SARS-CoV-2 RNA from site-collected NP swabs at entry, day 5, and day 15 among a subset of participants.

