9.6 Data management and monitoring

Whole blood for local safety labs will be collected and processed by Community Medical Center laboratory. This will include complete blood count with differential, comprehensive metabolic panel, western sedimentation rate, C-reactive protein, D-Dimer, Ferritin, and urine pregnancy test. If subject is known to be HIV positive, CD4/CD8 T cell count and HIV RNA standard assay will be completed. Local labs will be reviewed by the Investigator to monitor safety. Any abnormal values will be assessed for clinical significance by the Investigator. Any clinically significant laboratory results will be reported as an adverse event and assessed for causality.

Research labs that include nasopharyngeal (NP) swab for PCR + IgG, IgM, IgA, cytokine quantification; Saliva for host genomics will be collected, labeled with the subject ID, visit number and collection date. Saliva and NP swab will be frozen and stored in the -80 freezer located in the UCSF Fresno Clinical Research Center until requested by UCSF Core Immunology Lab (CIL). The freezer is locked and requires badge access. All blood collected for research only purposes will be sent to UCSF CIL laboratory by courier on the same day as collection.

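### The laboratory AE trigger in section 7.3.2 covers only rises, rests on an undefined SD, and is not reconciled with sections 7.2 and 9.6, so the entry rule for the Grade 2 or higher AE count is unclear

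*Combined protocol and SAP*

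**What the plan says.** Four places bear on when a laboratory value becomes an AE.

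- Section 7.2 (Definitions) lets an AE be "any unfavorable and unintended sign (including an abnormal laboratory finding, for example". It sets no direction and no threshold.
- Section 7.3.2 gives a numerical trigger: "Laboratory abnormalities will be reported as AEs if there is a 2 standard deviation increase above baseline".
- Section 9.6 gives a trigger by judgement: "Any clinically significant laboratory results will be reported as an adverse event and assessed for causality".
- Section 7.3.3 sets the severity scale: "Event severity will be graded using the DAIDS toxicity table".

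The results are used in two places. The safety endpoint counts graded events: section 6.1 has "Safety endpoints will include the total number of Grade 2 or higher events" and section 6.2.2 repeats this as a frequency. Section 6.2.4 compares AE rates between arms by Fisher's exact test, with no grade limit.

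The schedule in section 5.4.1 has one pre-dose safety draw, at Screen/Baseline, and post-baseline draws on Days 2, 5, 15 and 31. The Day 1 pre-dose list in section 5.5.2.1 adds a clinical laboratory collection without naming the tests.

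**The concern.** A count of AEs is only as well defined as the rule that decides what enters it. Here severity comes from a grading table, but entry comes from a trigger unrelated to that table. The trigger has three faults.

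- It looks in one direction. A fall in haemoglobin, platelets, neutrophils or lymphocytes cannot meet it, although the protocol schedules blood counts at four post-baseline visits, analyses lymphocyte counts (section 6.2.5) and names lymphopenia in its background (section 4.1.3).
- It cannot be applied as written, because the reader is not told whose SD to use or which draw is the baseline.
- It differs from the rule in section 9.6, and no order of precedence is given.

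Two staff members who both follow the protocol could log different events from the same laboratory report. The AE tables reviewed by the safety committee and compared between arms would then depend partly on who logged them.

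**Working it through.** The plan derives no figure from the 2 SD rule, so there is none to reproduce. The check asks what the rule yields under each SD it might mean.

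**1. Within-participant SD.** With one pre-dose value, n − 1 = 0 and the SD does not exist. If the unspecified Day 1 collection repeats the safety tests, n = 2. The 95% limits for the true SD, as multiples of the estimate, are √((n−1)/χ²) at the 0.975 and 0.025 quantiles on n − 1 degrees of freedom. For n = 2 they are 0.45 and 31.9. In a simulation of 1,000,000 draws with no drug effect and normal values, a new value exceeded the mean of two baseline values plus 2 SD in about 17.5% of tests.

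**2. Cohort SD.** The same formula gives 0.60 to 2.87 at n = 5 and 0.80 to 1.34 at n = 30. No such SD exists for the first participants. Section 6.2.5 itself treats D-dimer, ferritin, LDH and hs-CRP as right-skewed. The planning SD in section 6.1 is for IL-6, a research assay.

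**3. Chance of triggering with no drug effect.** Assume normal values, a between-participant SD, and a baseline-to-visit correlation ρ, which the documents do not give. A change then has SD √(2(1−ρ)) in between-participant units, so

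P(rise > 2 SD) = 1 − Φ(2/√(2(1−ρ))).

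Five markers (ESR, CRP, D-dimer, LDH, ferritin) over four post-baseline visits give 20 tests per participant.

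| ρ (assumed) | Per test | Expected per participant (× 20) |
|---|---|---|
| 0 | 7.9% | 1.57 |
| 0.5 | 2.3% | 0.46 |
| 0.8 | 0.08% | 0.016 |
| 0.9 | about 0 | about 0 |

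A known within-participant SD with a single baseline value gives 1 − Φ(2/√2) = 7.9% per test, as in the first row. The trigger's sensitivity therefore varies by analyte for reasons unrelated to toxicity.

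**4. Comparison with the one printed grade limit.** Section 8.2 labels AST or ALT above 5 × ULN as Grade 3. Section 5.3.2 admits participants with values up to 2 × ULN. The trigger point is baseline + 2 × SD. For assumed SDs of 0.25 to 2.0 × ULN:

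- from a baseline of 0.5 × ULN it runs from 0.5 + 0.5 = 1.0 to 0.5 + 4.0 = 4.5 × ULN;
- from a baseline of 2 × ULN it runs from 2 + 0.5 = 2.5 to 2 + 4.0 = 6.0 × ULN.

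At one extreme, a value at the limit of normal reaches the trigger. At the other, a value between 5 and 6 × ULN is Grade 3 but does not.

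**5. The rules side by side.**

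- Clinically significant platelet fall: not covered by 7.3.2, an AE under 9.6.
- Small rise beyond 2 SD, not clinically significant: an AE under 7.3.2, not under 9.6.
- Graded fall judged not clinically significant: not reported under 7.3.2 or 9.6. Section 7.2 would admit it, but that section defines an AE and gives no reporting instruction.

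**The case against.** The strongest reply is that section 7.3.2 says when a laboratory change will be reported, not that it is the only route. Read beside sections 7.2 and 9.6, it is one sufficient trigger among several. That stands in part: a reader might infer from the one-directional sentence that falls are never captured in this trial, and the documents do not support that. An investigator who judges a fall clinically significant must report it under section 9.6. But the reply does not supply an SD or a baseline draw, or say which rule governs when they disagree.

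A reader might also infer bias between arms. The trial is described as double-blind and placebo-controlled, and the same triggers apply to both arms. An unclear threshold costs consistency and sensitivity, and no mechanism favouring one arm is shown.

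A third inference is that the halting rule fails with the trigger. Criterion (d) of section 8.1 is "Two participants with a Grade 3 or higher lab toxicity for the same parameter associated with study product". It carries its own instruction to grade on the DAIDS table and does not require AE status under section 7.3.2. The scales differ, but no contradiction follows.

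Nor does the blood volume add a measured effect. The visit volumes do sum to the stated total (15 + 65 + 19 + 59 + 45 + 45 + 79 + 79 = 406 mL), but no expected haemoglobin change is given, and section 5.4 provides for monitoring and for reducing the volume.

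Finally, a reference or cohort SD could be applied to each participant if the plan named one. This is fair: the rule is undefined rather than impossible in every reading. Only the within-participant reading fails outright on the scheduled draws.

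**Conclusion.** The concern holds as a fault in a stated rule. The 2 SD trigger is one-directional, lacks an SD source and a baseline draw, and is unreconciled with the other two rules. The Grade 2 or higher count and the Fisher comparison inherit that ambiguity. Under the two reporting rules, a Grade 2 or higher fall depends on a judgement of clinical significance, while some trivial rises may enter automatically.

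The effect on the final counts cannot be given as one number, because it depends on an SD the plan does not name. The range above, from about 17.5% per unaffected test to almost zero, rests on normal values and assumed correlations and shows only how far the choice matters. The DAIDS table is not reproduced in the documents apart from the 5 × ULN limit, so which scheduled tests it grades, and in which directions, could not be checked.

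This should be corrected, but it does not undermine the trial's primary biomarker analysis.

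**What to change.** Delete the 2 SD sentence and reconcile sections 7.2, 7.3.2, 7.3.3 and 9.6 into one laboratory AE definition for the safety endpoint:

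- A post-dose value whose DAIDS grade is worse than at a named baseline draw, in either direction, is logged as an AE.
- The clinical-significance rule of section 9.6 is kept for analytes that the table does not grade.
- The grade is recorded on the AE log. Table 4 (section 5.7) now offers only mild, moderate and severe.

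State whether the Day 1 collection in section 5.5.2.1 includes safety tests, so that the baseline draw is unambiguous. Leave criterion 8.1(d) unchanged.

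The cost is protocol wording and one form field. The tests and the grading table are already in use. The downside is that more low-grade laboratory AEs may be logged, which would enter the AE comparison in section 6.2.4 because it has no grade limit.
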